4.5 Selection and Timing of Dose for Each Participant

The dosing schedule is detailed below in [Table 4.5-1](#).

All participants will be monitored continuously for AEs while on study treatment. Treatment modifications (eg, dose delay, reduction, retreatment, or discontinuation) will be based on specific laboratory and adverse event criteria, as described in [Sections 4.5.2, 4.5.3, 4.5.4, and 4.5.5](#).

Table 4.5-1: Dosing Schedule (Arm A 1 Cycle = 6 weeks, Arm B 1 Cycle = 3 weeks)

	Week 1 ± 3 Days ^d	Week 2 ± 3 Days ^d	Week 3 ± 3 Days ^d	Week 4 ± 3 Days ^d	Week 5 ± 3 Days ^d	Week 6 ± 3 Days ^d
Arm A: ^a Nivolumab 3 mg/kg Q2W + Ipilimumab 1 mg/kg Q6W ^b	Cycle 1, Day 1 Nivolumab + Ipilimumab		Cycle 1, Day 15 Nivolumab		Cycle 1 Day 29 Nivolumab	
Arm B: ^a EXTREME Regimen Cetuximab 400 mg/m ² initial dose then 250 mg/m ² weekly + Cis or Carbo + 5-FU Every 3 weeks for up to 6 Cycles followed by 250 mg/m ² Cetuximab weekly ^c 1 hour infusions	Cycle 1, Day 1 Cetuximab 2 hr infusion + Cis or Carbo 1 hr infusion + 5-FU (for 4 days, Day 1, 2, 3, 4)	Cycle 1, Day 8 Cetuximab 1 hr infusion	Cycle 1, Day 15 Cetuximab 1 hr infusion	Cycle 2, Day 1 Cetuximab 1 hr infusion + Cis or Carbo 1 hr infusion + 5-FU (for 4 days, Day 1, 2, 3, 4)	Cycle 2, Day 8 Cetuximab 1 hr infusion	Cycle 2, Day 15 Cetuximab 1 hr infusion

^a Arm A: Both nivolumab and ipilimumab should be administered as 30 minute infusions. Nivolumab is to be administered first. The second infusion will be ipilimumab and will start at least 30 minutes after completion of the nivolumab infusion

Arm B: Cetuximab is administered first followed by Cisplatin 100 mg/m² or Carboplatin (AUC 5) starting at least 1 hour after the completion of the Cetuximab infusion. 5-FU dose is 1000 mg/m² day 1 to day 4 (rounding of dosing for 5-FU is permitted per institutional standards).

^b Continues until disease progression, discontinuation due to unacceptable toxicity, withdrawal of consent, 24 months maximum from the first study treatment, or study closure

^c Cetuximab maintenance may be administered every 2 weeks, per local prescribing information.

^d ± 3 Days window applies to Arm A only

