4.5.2.1 Nivolumab and Ipilimumab (Arm A)

Dose delay criteria apply for all drug-related AEs. Treatment delay is up to 6 weeks for nivolumab and up to 12 weeks for ipilimumab from the last dose are allowable (any dose delays greater than these will require approval from the medical monitor). It is permissible in cases of a dose held due to AE to skip the dose in the cycle in order to bring the patient back on track with the next Cycle visit.

Tumor assessments for all participants should continue as per protocol even if dosing is delayed.

Nivolumab and ipilimumab administration should be delayed for the following:

- Grade 2 non-skin, drug-related AE, with the exception of fatigue
- Grade 2 drug-related creatinine, AST, ALT and/or Total Bilirubin abnormalities
- Grade 3 skin, drug-related AE
- Grade 3 drug-related laboratory abnormality, with the following exceptions:
 - Grade 3 lymphopenia or asymptomatic amylase or lipase does not require dose delay
 - Grade ≥ 3 AST, ALT, Total Bilirubin will require dose discontinuation (see section 4.5.5)
- Any adverse event, laboratory abnormality, or intercurrent illness which, in the judgment of the investigator, warrants delaying the dose of study medication.
- Participants receiving ipilimumab in combination with nivolumab that have drug-related toxicities that meet the criteria for dose delay, should have both drugs (ipilimumab and nivolumab) delayed until retreatment criteria are met. (Exceptions apply to the retreatment criteria after dose delay of ipilimumab and nivolumab for Grade ≤ 3 amylase and lipase

abnormalities that are not associated with symptoms or clinical manifestations of pancreatitis and that are attributed to ipilimumab alone.)

- Participants who require delay of nivolumab should be re-evaluated weekly or more frequently if clinically indicated and resume nivolumab dosing when re-treatment criteria are met.

Rescheduling:

- Nivolumab may be delayed until the next planned ipilimumab dose if the next ipilimumab dose is scheduled within the next 12 days. This will permit periodic ipilimumab dosing to be synchronized with nivolumab dosing.

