4.5.4 Criteria to Resume Dosing

4.5.4.1 Criteria to Resume Nivolumab Dosing (Arm A)

Participants may resume treatment with nivolumab when the drug-related AE(s) resolve(s) to Grade ≤ 1 or baseline, with the following exceptions:

- Participants may resume treatment in the presence of Grade 2 fatigue.

- Participants who have not experienced a Grade 3 drug-related skin AE may resume treatment in the presence of Grade 2 skin toxicity.
- Participants who received systemic corticosteroids for management of any drug-related toxicity must be off corticosteroids or have tapered down to an equivalent dose of prednisone ≤ 10 mg/day.
- For participants with Grade 2 AST, ALT and/or Total Bilirubin Abnormalities, dosing may resume when laboratory values return to baseline and management with corticosteroids, if needed, is complete.
- Drug-related pulmonary toxicity, diarrhea, or colitis must have resolved to baseline before treatment is resumed. Participants with persistent Grade 1 pneumonitis after completion of a steroid taper over at least 1 month may be eligible for retreatment if discussed with and approved by the BMS Medical Monitor.

Participants with drug-related endocrinopathies adequately controlled with only physiologic hormone replacement may resume treatment after consultation with the BMS Medical Monitor (or designee). Adrenal insufficiency requires discontinuation regardless of control with hormone replacement.

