4.5.4.2 Criteria to Resume Ipilimumab Dosing (Arm A)

Participants may resume treatment with nivolumab and ipilimumab when drug-related AE(s) resolve(s) to Grade 1 or baseline value, with the following exceptions:

- Participants may resume treatment in the presence of Grade 2 fatigue.
- Participants who have not experienced a Grade 3 drug-related skin AE may resume treatment in the presence of Grade 2 skin toxicity.
- Participants with baseline Grade 1 AST/ALT or total bilirubin who require dose delays for reasons other than a 2-grade shift in AST/ALT or total bilirubin may resume treatment in the presence of Grade 2 AST/ALT or total bilirubin.
- Participants with combined Grade 2 AST/ALT and total bilirubin values meeting discontinuation parameters ([Section 4.5.5.2](#)) should have treatment permanently discontinued.
- Drug-related pulmonary toxicity, diarrhea, or colitis must have resolved to baseline before treatment is resumed.
- Participants who received systemic corticosteroids for management of any drug-related toxicity must be off corticosteroids or have tapered down to an equivalent dose of prednisone ≤ 10 mg/day.
- Drug-related endocrinopathies adequately controlled with only physiologic hormone replacement may resume treatment after consultation with the BMS Medical Monitor.
- Dose delay of ipilimumab which results in no ipilimumab dosing for > 12 weeks requires ipilimumab discontinuation, with exceptions as noted in [Section 4.5.5.2](#).
- Ipilimumab may not be resumed sooner than 6 weeks (± 3 days) after the prior ipilimumab dose.
- In general, participants who meet criteria to resume ipilimumab will also have met criteria to resume nivolumab, so it should be feasible to synchronize dosing of both drugs when resuming

ipilimumab. In order to facilitate this, the dosing days of nivolumab and ipilimumab may be adjusted within the permitted ± 3 day window, as long as consecutive nivolumab doses are given at least 12 days apart.

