4.5.5.1 Nivolumab Dose Discontinuation (Arm A)

Treatment with nivolumab should be permanently discontinued for any of the following:

- Any Grade 2 drug-related uveitis, eye pain or blurred vision that does not respond to topical therapy and does not improve to Grade 1 severity within the re-treatment period OR requires systemic treatment
- Any Grade 3 non-skin, drug-related AE lasting > 7 days, or recurs with the following exceptions for laboratory abnormalities, diarrhea, colitis, neurologic toxicity, drug-related uveitis, pneumonitis, bronchospasm, hypersensitivity reactions, infusion reactions, and endocrinopathies:
 - Grade 3 drug-related diarrhea, colitis, neurologic toxicity, uveitis, pneumonitis, bronchospasm, myocarditis, hypersensitivity reaction, or infusion reaction of any duration requires discontinuation
 - Grade 3 drug-related endocrinopathies, adequately controlled with only physiologic hormone replacement do not require discontinuation. Adrenal insufficiency requires discontinuation regardless of control with hormone replacement.
 - Grade 3 drug-related laboratory abnormalities do not require treatment discontinuation except:
 - ◆ Grade 3 drug-related thrombocytopenia > 7 days or associated with bleeding requires discontinuation
 - ◆ Any drug-related liver function test (LFT) abnormality that meets the following criteria require discontinuation:
 - Grade ≥ 3 drug-related AST, ALT or Total Bilirubin requires discontinuation*
 - Concurrent AST or ALT > 3 x ULN and total bilirubin > 2x ULN
 - * In most cases of Grade 3 AST or ALT elevation, study treatment will be permanently discontinued. If the investigator determines a possible favorable benefit/risk ratio that warrants continuation of study treatment, a discussion between the investigator and the BMS Medical Monitor/designee must occur.
- Any Grade 4 drug-related adverse event or laboratory abnormality (including but not limited to creatinine, AST, ALT, or Total Bilirubin), except for the following events which do not require discontinuation:
 - Grade 4 neutropenia ≤ 7 days
 - Grade 4 lymphopenia or leukopenia or asymptomatic amylase or lipase

- Isolated Grade 4 electrolyte imbalances/abnormalities that are not associated with clinical sequelae and are corrected with supplementation/appropriate management within 72 hours of their onset

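### For adrenal insufficiency controlled on hormone replacement after a dose delay, Protocol 4.5.4.1 requires stopping while 4.5.4.2 lets both drugs restart, and no precedence is stated

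*Protocol*

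**What the plan says.** Protocol 4.5 ties the sections together: "Treatment modifications (eg, dose delay, reduction, retreatment, or discontinuation) will be based on specific laboratory and adverse event criteria". It points to 4.5.2 through 4.5.5 as a set and does not rank them.

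- **Delay (4.5.2.1).** Among the triggers is "Grade 2 non-skin, drug-related AE, with the exception of fatigue". Participants on the combination who meet a delay criterion "should have both drugs (ipilimumab and nivolumab) delayed until retreatment criteria are met".
- **Resuming nivolumab (4.5.4.1).** Endocrinopathies controlled on replacement may restart once the Medical Monitor has been consulted. The next sentence removes one of them: "Adrenal insufficiency requires discontinuation regardless of control with hormone replacement". No grade is attached.
- **Resuming ipilimumab (4.5.4.2).** The heading names ipilimumab, but the section opens "Participants may resume treatment with nivolumab and ipilimumab when drug-related AE(s) resolve(s) to Grade 1 or baseline value". One of its listed exceptions is "Drug-related endocrinopathies adequately controlled with only physiologic hormone replacement may resume treatment after consultation with the BMS Medical Monitor". Adrenal insufficiency is not mentioned.
- **Stopping nivolumab (4.5.5.1).** Under the Grade 3 bullet, endocrinopathies controlled on replacement "do not require discontinuation. Adrenal insufficiency requires discontinuation regardless of control with hormone replacement". The section also forbids continuing ipilimumab once nivolumab has been discontinued.
- **Stopping ipilimumab (4.5.5.2).** There is no rule specific to adrenal insufficiency.

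Protocol 6.7.1 lists adrenal insufficiency among the endocrine immune-mediated events, so it falls within the endocrinopathy wording of both resumption sections.

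**The concern.** The protocol singles out adrenal insufficiency as the one endocrinopathy for which good control on replacement does not permit further nivolumab. That restriction appears in the nivolumab resumption section and is missing from the next one, although the next one also speaks to restarting nivolumab. For the same participant and the same drug, one section mandates stopping and the other leaves restarting to a consultation.

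A site and Medical Monitor working from 4.5.4.2 as written could restart both drugs after an event for which 4.5.4.1 requires discontinuation. The consultation lowers that risk, but the visible text does not tell the Medical Monitor which rule governs. Under 4.5.4.1 the outcome is not discretionary; under 4.5.4.2 it is.

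**Working it through.** There is no figure in the plan to reproduce. The check applies the sections in order to one case: drug-related adrenal insufficiency at Grade 2, adequately controlled on physiologic replacement alone.

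1. **Delay.** The event is drug-related, not a skin event and not fatigue, so 4.5.2.1 delays both drugs. They stay on hold until the retreatment criteria are satisfied, which sends the reader to 4.5.4.1 and 4.5.4.2.
2. **4.5.4.1.** Nivolumab must be discontinued. If that is followed, 4.5.5.1 bars ipilimumab as well, and both drugs stop.
3. **4.5.4.2.** The case meets the endocrinopathy exception, so both drugs may restart after consultation.
4. **Discontinuation lists as a tie-breaker.** Neither 4.5.5.1 nor 4.5.5.2 has a Grade 2 criterion naming adrenal insufficiency. Both have a general criterion for events that the investigator judges to carry substantial clinical risk, but that is again discretionary.
5. **The ipilimumab bar as a tie-breaker.** It takes effect only after nivolumab has been discontinued, and that is the point in dispute.
6. **The link between the two resumption sections.** 4.5.4.2 says that participants who qualify to resume ipilimumab will generally also qualify for nivolumab. It then describes one exception, asymptomatic amylase or lipase elevation. A reader of that section is not prompted to go back to 4.5.4.1 for adrenal insufficiency.
7. **Steroid bullet.** 4.5.4.2 accepts up to 10 mg/day prednisone equivalent after steroid management of a toxicity, so being on a steroid does not in itself close the route.

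The same reading by grade:

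| Grade | Nivolumab | Ipilimumab | Settled by the text? |
|---|---|---|---|
| 2 | 4.5.4.1: stop. 4.5.4.2: may restart after consultation | 4.5.4.2: may restart after consultation. Barred only if nivolumab has been stopped | No |
| 3 | 4.5.5.1: stop | Barred once nivolumab is stopped | Yes |
| 4 | 4.5.5.1 alone: its endocrinopathy exception does not exclude adrenal insufficiency. 4.5.4.1: resumption barred | 4.5.5.2: stop (no endocrinopathy exception) | Ipilimumab: yes. Nivolumab: 4.5.5.1 alone is looser than at Grade 3, but the ungraded sentence in 4.5.4.1 still applies |

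**Size.** Arm A is about 930 / 2 = 465 participants. Those concerned are the subset with adrenal insufficiency, a resulting delay, control on replacement alone, and an attempt to resume. The documents give no incidence for this population, so no count follows.

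**The case against.** The strongest answer is that the sections can be applied together. 4.5.4.1 is mandatory and specific; 4.5.4.2 is permissive and general. Stopping complies with both, restarting breaches the first, and rules that apply cumulatively need no ranking. The sentence in 4.5.4.2 relating the two sets of criteria also treats the nivolumab criteria as a separate test, and its qualifier admits exceptions. This is a sensible reading and probably the intended one. It remains an inference: 4.5.4.2 itself speaks to restarting nivolumab, and the only exception it goes on to describe concerns pancreatic enzymes.

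It can also be said that the omission is consistent drafting, since the nivolumab sections carry the adrenal rule and the ipilimumab sections do not. Against this, the 4.5.4.2 list does contain a must-stop item, beginning "Participants with combined Grade 2 AST/ALT and total bilirubin values meeting discontinuation parameters". That comparison is weak evidence, because the item only refers back to limits in 4.5.5.2, which has no adrenal rule to refer to. The point does not depend on it.

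The endocrinopathy algorithm in Appendix 2 is a figure not shown here, and the Investigator Brochures are not available. Either may give direction. Nothing is claimed about their content; Appendix 2 describes its algorithms as guidance.

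A reader might go further and infer that the protocol allows nivolumab to continue after Grade 4 adrenal insufficiency although it must stop at Grade 3. The documents do not support that. The Grade 4 exception in 4.5.5.1 gives thyroid and glucose disorders as examples, is discretionary and needs Medical Monitor approval. The adrenal sentence in 4.5.4.1 has no grade limit, so it bars resumption at Grade 4 too. What remains is that 4.5.5.1, read on its own, is looser at Grade 4 than at Grade 3.

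**Conclusion.** The conflict is real but narrow. It applies to drug-related adrenal insufficiency that has led to a dose delay and is adequately controlled on physiologic replacement alone, and it is clearest at Grade 2. Grade 3 is settled. The conclusion rests on the visible text and on taking the opening sentence of 4.5.4.2, not its heading, as defining its scope.

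It is a wording inconsistency with a participant-safety consequence and should be corrected. It gives no ground to infer that anyone was restarted wrongly, since the documents hold no conduct data. OS, alpha and power are unaffected, and the SAP tables need no change. SAP 7.6.7 already plans a summary of re-challenge by immune-mediated event category, which would report such restarts only after the fact.

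**What to change.** Add this sentence to the endocrinopathy bullet of Protocol 4.5.4.2: "Adrenal insufficiency requires discontinuation regardless of control with hormone replacement". If the sponsor does intend resumption to be possible, it should say so and amend 4.5.4.1 instead, so that the two sections agree.

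As an optional consistency edit, state in the Grade 4 endocrinopathy exception of 4.5.5.1 that it does not apply to adrenal insufficiency. Repeating the sentence in 4.5.5.2 is also optional.

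The cost is one sentence, plus a short exclusion if the optional edit is made, by clarification letter or in the next revision. Data collection and analysis do not change.

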4.5.5 Treatment Discontinuation Criteria

For all participants, global deterioration of health status requiring discontinuation of treatment without objective evidence of disease progression at that time will be captured on the health outcomes questionnaires. Tumor assessments for participants who discontinue study treatment or who have clinically progressed without radiographic progression, should continue as per protocol until radiographic progression per RECIST 1.1 is determined.

4.5.5.1 Nivolumab Dose Discontinuation (Arm A)

Treatment with nivolumab should be permanently discontinued for any of the following:

- Any Grade 2 drug-related uveitis, eye pain or blurred vision that does not respond to topical therapy and does not improve to Grade 1 severity within the re-treatment period OR requires systemic treatment
- Any Grade 3 non-skin, drug-related AE lasting > 7 days, or recurs with the following exceptions for laboratory abnormalities, diarrhea, colitis, neurologic toxicity, drug-related uveitis, pneumonitis, bronchospasm, hypersensitivity reactions, infusion reactions, and endocrinopathies:
 - Grade 3 drug-related diarrhea, colitis, neurologic toxicity, uveitis, pneumonitis, bronchospasm, myocarditis, hypersensitivity reaction, or infusion reaction of any duration requires discontinuation
 - Grade 3 drug-related endocrinopathies, adequately controlled with only physiologic hormone replacement do not require discontinuation. Adrenal insufficiency requires discontinuation regardless of control with hormone replacement.
 - Grade 3 drug-related laboratory abnormalities do not require treatment discontinuation except:
 - ◆ Grade 3 drug-related thrombocytopenia > 7 days or associated with bleeding requires discontinuation
 - ◆ Any drug-related liver function test (LFT) abnormality that meets the following criteria require discontinuation:
 - Grade ≥ 3 drug-related AST, ALT or Total Bilirubin requires discontinuation*
 - Concurrent AST or ALT > 3 x ULN and total bilirubin > 2x ULN
 - * In most cases of Grade 3 AST or ALT elevation, study treatment will be permanently discontinued. If the investigator determines a possible favorable benefit/risk ratio that warrants continuation of study treatment, a discussion between the investigator and the BMS Medical Monitor/designee must occur.
- Any Grade 4 drug-related adverse event or laboratory abnormality (including but not limited to creatinine, AST, ALT, or Total Bilirubin), except for the following events which do not require discontinuation:
 - Grade 4 neutropenia ≤ 7 days
 - Grade 4 lymphopenia or leukopenia or asymptomatic amylase or lipase

- Isolated Grade 4 electrolyte imbalances/abnormalities that are not associated with clinical sequelae and are corrected with supplementation/appropriate management within 72 hours of their onset
- Grade 4 drug-related endocrinopathy adverse events, such as, hyper- or hypothyroidism, or glucose intolerance, which resolve or are adequately controlled with physiologic hormone replacement (corticosteroids, thyroid hormones) or glucose-controlling agents, respectively, may not require discontinuation after discussion with and approval from the BMS Medical Monitor.
- Any event that leads to delay in dosing lasting > 6 weeks from the previous dose requires discontinuation, with the following exceptions:
 - Dosing delays to allow for prolonged steroid tapers to manage drug-related adverse events are allowed.
 - Dosing delays lasting > 6 weeks from the previous dose that occur for non-drug-related reasons may be allowed if approved by the BMS Medical Monitor (or designee).
- Any adverse event, laboratory abnormality, or intercurrent illness which, in the judgment of the Investigator, presents a substantial clinical risk to the participant with continued nivolumab dosing.
- Prior to re-initiating treatment in a participant with a dosing delay lasting > 6 weeks, the BMS Medical Monitor (or designee) must be consulted. Tumor assessments should continue as per protocol even if dosing is delayed. Periodic study visits to assess safety and laboratory studies should also continue every 6 weeks or more frequently if clinically indicated during such dosing delays.

The assessment for discontinuation of nivolumab should be made separately from the assessment made for discontinuation of ipilimumab. Although there is overlap among the discontinuation criteria, if discontinuation criteria are met for ipilimumab but not for nivolumab, treatment with nivolumab may continue if ipilimumab is discontinued.

If a participant meets criteria for discontinuation and investigator is unable to determine whether the event is related to both or one study drug, the participant should discontinue both nivolumab and ipilimumab and be taken off the treatment phase of the study. Continuation of ipilimumab after discontinuation of nivolumab is not allowed on study.

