- Ipilimumab should be dosed at the specified interval regardless of any delays in intervening nivolumab doses. However, in order to maintain periodic synchronized dosing of ipilimumab and nivolumab, the dosing days of nivolumab and ipilimumab may be adjusted within the permitted ± 3 day window, as long as consecutive nivolumab doses are given at least 12 days apart. Ipilimumab may be delayed beyond the 3 day window if needed to synchronize with the next nivolumab dose.
- If an ipilimumab dose is delayed beyond 6 weeks from the prior ipilimumab dose, then subsequent ipilimumab doses should be rescheduled to maintain the 6 week interval between consecutive ipilimumab doses.
- A dose delay of ipilimumab which results in no ipilimumab dosing for > 12 weeks requires ipilimumab discontinuation, with exceptions as noted in [Section 4.5.5.2](#).

For both nivolumab and ipilimumab: A dose given more than 3 days after the intended dose date will be considered a dose delay. Longer delays may be allowed following discussion with the Study Director/Medical Monitor.

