4.5.5.2 Ipilimumab Dose Discontinuation (Arm A)

Ipilimumab should be permanently discontinued if any of the following criteria are met:

- Any Grade \geq 2 drug-related uveitis or eye pain or blurred vision that does not respond to topical therapy and does not improve to Grade 1 severity within 2 weeks OR requires systemic treatment;
- Any Grade \geq 3 bronchospasm or other hypersensitivity reaction;
- Any other Grade 3 non-skin, drug-related adverse event with the following exceptions for laboratory abnormalities, Grade 3 nausea and vomiting, Grade 3 neutropenia and thrombocytopenia, and symptomatic endocrinopathies which resolved (with or without hormone substitution);

- Any drug-related liver function test (LFT) abnormality that meets the following criteria require discontinuation:
 - AST or ALT > 8x ULN
 - Total bilirubin > 5 x ULN
 - Concurrent AST or ALT > 3 x ULN and total bilirubin > 2 x ULN
- Any Grade 4 drug-related adverse event or laboratory abnormality, except for the following events, which do not require discontinuation:
 - Grade 4 neutropenia ≤ 7 days
 - Grade 4 lymphopenia or leukopenia
 - Isolated Grade 4 amylase or lipase abnormalities which are not associated with symptoms or clinical manifestations of pancreatitis.
 - Isolated Grade 4 electrolyte imbalances/abnormalities that are not associated with clinical sequelae and are corrected with supplementation/appropriate management within 72 hours of their onset
- Any treatment delay resulting in no ipilimumab dosing for > 12 weeks with the following exceptions: Dosing delays to manage drug-related adverse events, such as prolonged steroid tapers, are allowed. Prior to re-initiating treatment in a participant with a dosing delay lasting > 12 weeks, the BMS medical monitor must be consulted. Tumor assessments should continue as per protocol even if dosing is delayed.
- Dosing delays resulting in no ipilimumab dosing for > 12 weeks that occur for non-drug-related reasons may be allowed if approved by the BMS medical monitor. Prior to re-initiating treatment in a participant with a dosing delay lasting > 12 weeks, the BMS medical monitor must be consulted. Tumor assessments should continue as per protocol even if dosing is delayed.
- Any adverse event, laboratory abnormality, or intercurrent illness which, in the judgment of the Investigator, presents a substantial clinical risk to the participant with continued ipilimumab dosing

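### A drug-related nivolumab hold over 6 weeks without a steroid taper is open to approval under Protocol 4.5.2.1 but is a required permanent stop under 4.5.5.1

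*Protocol*

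**What the plan says.** Protocol Section 4.5.2.1 (dose delays, Arm A) sets its scope in its first sentence: "Dose delay criteria apply for all drug-related AEs". It then gives the limits: "Treatment delay is up to 6 weeks for nivolumab and up to 12 weeks for ipilimumab from the last dose are allowable". In parentheses it adds that "any dose delays greater than these will require approval from the medical monitor". The section closes with a sentence for both drugs: "Longer delays may be allowed following discussion with the Study Director/Medical Monitor". Neither statement on longer delays distinguishes causes.

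Section 4.5.5.1 (nivolumab discontinuation, Arm A) begins: "Treatment with nivolumab should be permanently discontinued for any of the following". One item on its list is: "Any event that leads to delay in dosing lasting > 6 weeks from the previous dose requires discontinuation, with the following exceptions". The first exception is a prolonged steroid taper used to manage a drug-related event. The second is a non-drug-related reason, if the medical monitor approves. A later bullet requires consultation with the medical monitor before restarting after more than 6 weeks. The section also states: "Continuation of ipilimumab after discontinuation of nivolumab is not allowed on study".

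Section 3.5 lists the reasons for which study treatment must stop, and includes those in Section 4.5.5 by reference.

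For ipilimumab, Section 4.5.2.1 requires discontinuation after more than 12 weeks without a dose and refers to Section 4.5.5.2 for exceptions. That section says: "Dosing delays to manage drug-related adverse events, such as prolonged steroid tapers, are allowed".

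**The concern.** The delay section and the discontinuation section use the same 6-week limit, counted from the same point (the last nivolumab dose), but treat what lies beyond it differently. In 4.5.2.1 an approval route is open to any delay. In 4.5.5.1 approval is offered only when the cause is not drug-related, and the only drug-related delay that escapes discontinuation is one for a steroid taper. A drug-related event that resolves slowly and is managed without a taper falls between the two.

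At stake is whether a participant is re-dosed after toxicity or permanently loses the experimental regimen. If medical monitors or sites resolve the conflict differently, similar participants will be treated differently. Arm A exposure and the recorded reasons for discontinuation would then partly reflect which section was followed.

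**Working it through.** No figure in the plan is involved, so the check is a comparison of text. It takes nivolumab delays of more than 6 weeks since the last dose and applies each section to each possible cause.

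| Cause of the delay | Section 4.5.2.1 | Section 4.5.5.1 | Result |
|---|---|---|---|
| Drug-related, prolonged steroid taper | Possible with approval or discussion | Excepted from discontinuation | Agree that treatment may resume |
| Drug-related, no steroid taper | Possible with approval or discussion | No exception applies; discontinuation required | Conflict |
| Not drug-related | Possible with approval or discussion | Possible with approval | Agree |

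The conflict is confined to the second row. Four further checks fix its scope.

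1. **The consultation bullet in 4.5.5.1.** It stands outside the list of exceptions and sets a step to take before restarting. It has a full purpose for the first and third rows, so it need not be read as a further exception for the second.

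2. **Ipilimumab.** For gaps over 12 weeks, 4.5.2.1 itself requires discontinuation and refers to 4.5.5.2 (Section 4.5.4.2 repeats this). The exception in 4.5.5.2 covers delays to manage drug-related events in general, with steroid tapers only as an example. The second-row conflict therefore has no ipilimumab counterpart. The nivolumab sentences in 4.5.2.1 carry no matching reference to 4.5.5.1.

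3. **Effect on the regimen.** Section 4.5.2.1 generally holds both drugs together when delay criteria are met, and 4.5.5.1 bars ipilimumab after nivolumab is discontinued. In the second row, the 4.5.5.1 reading ends both drugs.

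4. **When the limit is reached.** Nivolumab is given every 2 weeks and the limit runs from the last dose given, so it is reached 6 − 2 = 4 weeks after the first missed dose.

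The two drugs' limits also run from different dates. Table 4.5-1 gives nivolumab on Days 1, 15 and 29 of a 6-week cycle and ipilimumab on Day 1. With ipilimumab last given on Day 1, its 12-week limit falls on Day 1 + 84 = Day 85. The nivolumab 6-week limit falls on:

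- Day 1 + 42 = Day 43 if nivolumab was last given on Day 1, leaving 85 − 43 = 42 days (6 weeks) to the ipilimumab limit;
- Day 15 + 42 = Day 57 if last given on Day 15, leaving 28 days (4 weeks);
- Day 29 + 42 = Day 71 if last given on Day 29, leaving 14 days (2 weeks).

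The period in which only the nivolumab limit has passed is thus 2 to 6 weeks, depending on the last dose.

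**The case against.** The best defence is that the sections can be read together. Section 3.5 makes the 4.5.5 reasons compulsory, whereas 4.5.2.1 is only permissive, so 4.5.5.1 could be taken as the specific rule that limits a general permission. Section 4.5.2.1 defers to 4.5.5 elsewhere, for Grade 3 or higher liver tests and for ipilimumab gaps over 12 weeks. This has weight: the texts are a permission set against a requirement, not two equal commands. It does not settle the matter. Neither Section 3.5 nor 4.5.5.1 withdraws the approval route, and 4.5.2.1 offers that route in a section that covers all drug-related events. Where the drafters meant 4.5.2.1 to give way they wrote a cross-reference, and the nivolumab sentences have none.

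The affected group is also narrow. Other items in 4.5.5.1 already stop most Grade 3 non-skin events lasting over 7 days, Grade 3 or higher liver tests in most cases, and most Grade 4 events. What remains is mainly lower-grade, skin, laboratory or hormone-controlled endocrine events held for a long time without a taper. This stands and limits the size of the point.

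A reader might infer three stronger things, which the documents do not support.

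- *That sites may choose freely between the sections.* Under 4.5.2.1 a longer delay needs the medical monitor's approval or a discussion, and under 4.5.5.1 the monitor must be consulted before restart. A compliant site involves the monitor either way. What is missing is a single rule for the monitor to apply.
- *That ipilimumab has the same conflict, or that its 12-week limit can never operate.* The cross-reference to 4.5.5.2 removes the first. As to the second, Section 4.5.4.2 lets nivolumab resume before ipilimumab for certain amylase or lipase abnormalities, so the ipilimumab limit can still apply. Different limits for drugs with different dosing intervals are not in themselves an error.
- *That there is a fixed window of 6 to 12 weeks in which one text allows dosing and the other forbids it.* Each limit runs from that drug's own last dose, so there is no such common window.

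**Conclusion.** The point holds for nivolumab in Arm A only, and only for drug-related delays over 6 weeks without a steroid taper. For those, Section 4.5.2.1 leaves resumption open to approval and Section 4.5.5.1, backed by Section 3.5, requires a permanent stop that takes ipilimumab with it.

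The number of participants affected cannot be derived from the documents. The conclusion assumes that the two exceptions listed in 4.5.5.1 are complete, as its wording indicates, and that no precedence between the sections is set elsewhere; none was found.

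The consequence is for participant safety, Arm A exposure and discontinuation data. Overall survival is analysed as randomized, and its alpha, power and event counts do not change. Because a treatment-stopping rule is involved and the correction is cheap, the change should be made.

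**What to change.** Reconcile Sections 4.5.2.1 and 4.5.5.1 so that one rule covers drug-related nivolumab delays over 6 weeks from the last dose without a steroid taper. Which rule applies is for the clinical team to decide; this review proposes neither. Once it is settled, add to the nivolumab text in 4.5.2.1 a cross-reference to 4.5.5.1, matching the one that ipilimumab already has to 4.5.5.2, so that sites and the medical monitor reach the same text from either section.

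The cost is a wording change in the protocol and a notice to sites. No analysis, sample size or data collection changes.
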